## Appendix 1: Schedule of Activities

---

- g A FFPE tumor tissue block or a minimum of 10 freshly cut, unstained, serial slides from patients will be submitted at screening. Cytologic or fine-needle aspiration samples are not acceptable. Tumor tissue from bone metastases is not acceptable. If archival tissue is insufficient, a fresh tumor biopsy meeting the minimum requirement may be obtained with if the patient's consent.
- h Concomitant medications include any medication (e.g., prescription drugs, over-the-counter drugs, vaccines, herbal or homeopathic remedies, nutritional supplements) used by a patient from 14 days prior to prior to initiation of study treatment until 28 days after the last dose of study treatment.
- i After informed consent has been obtained but prior to initiation of study treatment, only serious adverse events caused by a protocol-mandated intervention should be reported. After initiation of study drug, all adverse events will be reported until 28 days after the final dose of study treatment. After this period, the Sponsor should be notified if the investigator becomes aware of any serious adverse event that is believed to be related to prior study treatment. The investigator should follow each adverse event until the event has resolved to baseline grade or better, the event is assessed by the investigator as stable and no further changes are expected, the patient is lost to follow-up, or the patient withdraws consent. Every effort should be made to follow all serious adverse events considered by the investigator to be related to study treatment or trial-related procedures until a final outcome can be reported.
- j A complete physical examination includes evaluation of the head, eyes, ears, nose, and throat, and the cardiovascular, dermatological, musculoskeletal, respiratory, gastrointestinal, genitourinary, and neurological systems. Record abnormalities observed at baseline on the General Medical History and Baseline Conditions eCRF. At study discontinuation visit, record new or worsened clinically significant abnormalities on the Adverse Event eCRF.
- k Perform a limited, symptom-directed physical examination at specified timepoints or as clinically indicated. Record new or worsened clinically significant abnormalities on the Adverse Event eCRF.
- l Vital signs include respiratory rate, pulse (heart) rate, and systolic and diastolic blood pressures while the patient is in a seated position, and temperature. Record abnormalities observed at baseline on the General Medical History and Baseline Conditions eCRF. At subsequent visits, record new or worsened clinically significant abnormalities on the Adverse Event eCRF.
- m ECG recordings will be obtained as part of the screening assessment, as clinically indicated during study treatment, and at the end of treatment visit.
- n If the progression disease will be based on PSA at screening, at least two PSA samples (obtained at least 1 week apart) will be assessed locally at screening for confirmation of eligibility (if no data are available prior to screening). Central testing required for Day 1 of each cycle and at study treatment discontinuation. Patients who discontinue study treatment prior to 12 weeks of treatment should have an assessment of PSA in post-treatment follow-up period that is at least 12 weeks following the start of study treatment if they have not yet started another systemic treatment.
- o For patients with prostate cancer, serum testosterone samples will be assessed locally at screening for determination of eligibility and at study treatment discontinuation to confirm testosterone remains at castration level.

## Appendix 1: Schedule of Activities

---

- p Hematology includes WBC count, RBC count, hemoglobin, hematocrit, platelet count, and differential count (neutrophils, eosinophils, basophils, monocytes, lymphocytes, and other cells).
- q Test may be performed  $\leq 96$  hours prior to dosing for each clinic visit during study treatment; screening assessments performed  $\leq 96$  hours prior to dosing on Day 1 of Cycle 1 do not have to be repeated on Day 1 of Cycle 1.
- r For all clinic visits during study treatment, the glucose level of the patient must be performed  $\leq 96$  hours prior to dosing and must be reviewed prior to further ipatasertib administration and prior to discharge from the clinic. Blood glucose may be obtained by a glucometer (fingerstick). For fasting blood glucose, patients should fast  $\geq 8$  hours prior to testing.
- s Nonfasting blood glucose samples are to be collected on PK collection days at the same timepoints listed for ipatasertib PK sample in [Appendix 3](#). Patients will be required to eat a meal approximately 30 minutes postdose on Day 1 of Cycle 1 and Day 15 of Cycle 1. The exact date may be shifted by  $\pm 7$  days or more to match the PK collection per [Appendix 3](#).
- t Chemistry panel includes sodium, potassium, chloride, magnesium, bicarbonate, BUN (or urea), creatinine, total protein, albumin, calcium, and liver function test panel (total and direct bilirubin, alkaline phosphatase, ALT, AST, and LDH).
- u Women of childbearing potential must have a negative serum pregnancy test result within 3 days prior to initiation of study drug.
- v Includes dipstick (pH, specific gravity, glucose, protein, ketones, blood).
- w Tumor assessments should include the chest, abdomen, and pelvis (and other body regions if clinically indicated) at screening and at subsequent tumor assessments, even if there are no detectable lesions at baseline. CT scans are the preferred imaging modality for tumor assessments. MRI scans may be substituted for CT scans and the same imaging method used at screening should be used throughout the study. Responses will be assessed according to RECIST v1.1. For patients with prostate cancer, CT or MRI assessments for soft tissue lesions should continue per [Section 4.5.6](#) until radiographically assessed disease progression regardless of study treatment discontinuation.
- x Tumor assessments should be performed  $\pm 2$  weeks of the scheduled cycles for the first 6 months and then every 12 weeks (or 3 cycles), thereafter, and as clinically indicated. At the investigator's discretion, imaging may be repeated at any time if progressive disease is suspected. The frequency of tumor assessments may be further reduced after 1 year with approval of the Medical Monitor. Tumor assessments at the end of treatment visit are not required if radiographic disease progression per RECIST v1.1 or PCWG3 criteria (if applicable) has been documented previously or if the last tumor assessments were performed  $< 4$  weeks prior to the end of treatment visit. If an initial CR or PR is noted, confirmatory scans should be performed  $\geq 4$  weeks later. In the case of SD, follow-up measurements should have met the SD criteria at least once after study entry at a minimum interval of no less than 4 weeks. For patients with prostate cancer, tumor assessments should continue per above schedule until radiographically assessed disease progression even if study treatment has been discontinued for other reasons. For patients with breast and ovarian cancer, continuation of tumor assessments is preferred but not required.

## Appendix 1: Schedule of Activities

---

- y A technetium bone scan will be performed at screening (within 42 days before starting study treatment) to evaluate for the presence of bone metastases. For patients with prostate cancer, bone scans must continue per Section 4.5.6 until radiographically assessed disease progression regardless of study treatment discontinuation. For patients with breast and ovarian cancer, a bone scan is needed for screening assessment. For patients with known or suspected bone metastases, follow up bone scans should be done at time of tumor assessments and at the study treatment discontinuation visit (unless followed by other imaging modalities).
- z If dosing of study treatment is withheld for any reason, study day count should continue and the omitted dose will not be made up and will be reported on the eCRF as “not administered” for that day. *For patients enrolled in Part 1, rucaparib should be started in the evening of Day 1 of Cycle 1 following collection of all ipatasertib PK samples.*
- aa See [Appendix 2](#) for PK sample collection.
- bb Samples will be collected only at sites with local regulatory authority approval. See [Appendix 3](#) for further details
- cc The optional RBR blood sample (for DNA extraction) requires an additional informed consent and can be collected at any time during the course of the study. See [Appendix 3](#) for further details.
- dd The optional predose tumor biopsy specimen will be obtained after eligibility criteria have been fulfilled and prior to Day –7 of Cycle 1. A subsequent biopsy will be performed on either Day –1 or *Day 1* of Cycle 1, prior to the administration of rucaparib. An additional biopsy will be collected on Day 15 of Cycle 2. See the laboratory manual for details.
- ee The optional predose tumor biopsy specimen will be obtained after eligibility criteria have been fulfilled and prior to Day 1 of Cycle 1. An additional biopsy will be collected on Day 15 of Cycle 2. See the laboratory manual for details.

## Appendix 2

### Schedule of Pharmacokinetic Samples (Parts 1 and 2)

**Table 1 Schedule of Pharmacokinetic Samples in Dose-Escalation Phase (Part 1)**

Visit	Timepoint	Sample Type
Cycle 1, Day -7 a	Prior to first ipatasertib administration	Ipatasertib PK (Plasma)
Cycle 1, Day 1 b	1 hour ( $\pm$ 10 min) post-ipatasertib dose	Ipatasertib PK (Plasma)
	2 hour ( $\pm$ 10 min) ipatasertib post-dose	Ipatasertib PK (Plasma)
	3 hour ( $\pm$ 30 min) ipatasertib post-dose	Ipatasertib PK (Plasma)
	5 hour ( $\pm$ 30 min) ipatasertib post dose	Ipatasertib PK (Plasma)
Cycle 1, Day 15 c	Prior to ipatasertib and rucaparib administration	Ipatasertib PK (Plasma) Rucaparib PK (Plasma)
	1 hour ( $\pm$ 10 min) post-ipatasertib dose	Ipatasertib PK (Plasma)
	2 hour ( $\pm$ 10 min) post-ipatasertib dose	Ipatasertib PK (Plasma)
	3 hour ( $\pm$ 30 min) post-ipatasertib dose	Ipatasertib PK (Plasma)
	5 hour ( $\pm$ 30 min) post-ipatasertib dose	Ipatasertib PK (Plasma)
Cycle 2, Day 1 c	Prior to ipatasertib and rucaparib administration	Ipatasertib PK (Plasma) Rucaparib PK (Plasma)
Cycle 2, Day 15 c	Prior to ipatasertib and rucaparib administration	Ipatasertib PK (Plasma) Rucaparib PK (Plasma)

*CPI = coproporphyrin I; CP III = coproporphyrin III; PK = pharmacokinetic.*

*Note: Ipatasertib PK samples will be collected for analysis of both ipatasertib and its metabolite G-037720.*

- a The Cycle 1, Day -7 assessment should be done prior to start of ipatasertib and rucaparib administration. The sample will be used for measurement of baseline CPI and CP III levels prior to treatment initiation.
- b PK sampling on Day 1 of Cycle 1 should be completed before initiation of rucaparib therapy.
- c If a patient's ipatasertib or rucaparib treatment has been interrupted for  $\geq$  1 day immediately before the Cycle 1, Day 15 and Cycle 2 visits, PK samples may be rescheduled to another day when both study treatments have been given for at least 5 consecutive days. Cycle 1, Day 15 and Cycle 2 visit assessments during the treatment period should be performed within  $\pm$  7 days of the scheduled date. Study assessments may be delayed or moved ahead of the window to accommodate holidays, vacations, and unforeseen delays.

**Appendix 2: Schedule of Pharmacokinetic Samples (Parts 1 and 2)**

---

**Table 2 Schedule of Pharmacokinetic Samples in Dose-Expansion Phase (Part 2)**

Visit	Timepoint	Sample Type
Cycle 1, Day 15	Prior to ipatasertib and rucaparib administration	Ipatasertib PK (Plasma) Rucaparib PK (Plasma)
Cycle 2, Day 1 a	Prior to ipatasertib and rucaparib administration	Ipatasertib PK (Plasma) Rucaparib PK (Plasma)
Cycle 2, Day 15 a	Prior to ipatasertib and rucaparib administration	Ipatasertib PK (Plasma) Rucaparib PK (Plasma)

PK = pharmacokinetic.

Notes: Except for Cycle 1, Day 1, all other study visits and assessments during the treatment period should be performed within  $\pm 7$  days of the scheduled date. Study assessments may be delayed or moved ahead of the window to accommodate holidays, vacations, and unforeseen delays.

Ipatasertib PK samples will be collected for analysis of both ipatasertib and its metabolite G-037720.

a If a patient's ipatasertib or rucaparib treatment has been interrupted for  $\geq 1$  day immediately before the visit, PK samples may be rescheduled to another day when both study treatments have been given for at least 5 consecutive days.

### Appendix 3 Schedule of Biomarker Samples (Parts 1 and 2)

**Table 1 Schedule of Biomarker Samples in Dose-Escalation Phase (Part 1)**

Visit	Timepoint	Sample Type
Cycle 1, Day -7 (Part 1)	Prior to first ipatasertib administration	Blood sample for WGS control
		Blood sample for pharmacogenomics
		Plasma sample for somatic tumor mutations
		Plasma sample for exploratory biomarkers
		Blood sample for RBR (for DNA extraction; optional)
Cycle 2, Day 1	Prior to ipatasertib and rucaparib administration	Plasma sample for somatic tumor mutations
		Plasma sample for exploratory biomarkers
Treatment discontinuation		Plasma sample for somatic tumor mutations
		Plasma sample for exploratory biomarkers

RBR = *Research* Biosample Repository; WGS = whole genome sequencing.

**Table 2 Schedule of Biomarker Samples in Dose-Expansion Phase (Part 2)**

Visit	Timepoint	Sample Type
Cycle 1, Day 1	Prior to first ipatasertib administration	Blood sample for WGS control
		Blood sample for pharmacogenomics
		Plasma sample for somatic tumor mutations
		Plasma sample for exploratory biomarkers
		Blood sample for RBR (for DNA extraction; optional)
Cycle 2, Day 1	Prior to ipatasertib and rucaparib administration	Plasma sample for somatic tumor mutations
		Plasma sample for exploratory biomarkers
Treatment discontinuation		Plasma sample for somatic tumor mutations
		Plasma sample for exploratory biomarkers

[figure not shown]
RBR = *Research* Biosample Repository; WGS = whole genome sequencing.

## Appendix 4

### Eastern Cooperative Oncology Group Performance Status Scale

Grade	Description
0	Fully active, able to carry on all predisease performance without restriction
1	Restricted in physically strenuous activity but ambulatory and able to carry out work of a light or sedentary nature; e.g., light housework or office work
2	Ambulatory and capable of all self-care but unable to carry out any work activities; up and about > 50% of waking hours
3	Capable of only limited self-care, confined to a bed or chair > 50% of waking hours
4	Completely disabled; cannot carry on any self-care; totally confined to bed or chair
5	Dead

## Appendix 5 PSA Progression Eligibility Criteria

PSA=prostate-specific antigen.

Eligibility based on prostate-specific antigen (PSA) changes. The reference value (#1) is the last PSA measured before increases are documented, with subsequent values obtained a minimum of 1 week apart. If the PSA at time point 3 (value #3A) is greater than that at point 2, then eligibility has been met. If the PSA is not greater than point 2 (value #3B), but value #4 is, the patient is eligible assuming that other criteria are met, if values 3A or #4 are 1 ng/mL or higher.

### **REFERENCES**

## Appendix 6

### Criteria for Radiographic Progression per Prostate Cancer Working Group 3

Date Progression Detected (Visit) a	Criteria for Progression	Criteria for Confirmation of Progression (requirement and timing)	Criteria for Documentation of Disease Progression on Confirmatory Scan
Week 8	Bone lesions: Two or more new lesions compared to baseline bone scan by PCWG3.  Soft tissue lesions: Progressive disease on CT or MRI scan by RECIST v1.1 b	Timing: at least 6 weeks after progression identified or at Week 16 visit. c  No confirmatory scan required for soft tissue disease progression.	Two or more new bone lesions on bone scan (compared to Week 8 scan).  NA
Week 16 or later	Bone lesions: Two or more new lesions on bone scan compared to Week 8 bone scan.  Soft tissue lesions: Progressive disease on CT or MRI scan by RECIST v1.1. b	Timing: at least 6 weeks after progression identified; required for bone lesions observed on bone scan c  No confirmatory scan required for soft tissue disease progression.	Persistent d or increased number of bone lesions on bone scan compared to prior scan.  NA

CT=computed tomography; MRI=magnetic resonance imaging; NA=not applicable; PCWG3=Prostate Cancer Working Group 3, RECIST v1.1=Response Evaluation Criteria in Solid Tumors, Version 1.1.

Note: Adapted from Scher et al. 2016.

- a Progression detected by bone scan at an unscheduled visit will require a confirmatory scan at least 6 weeks later and should follow confirmation criteria outlined in the table for the next scheduled scan. Progression detected by bone scan at an unscheduled visit prior to Week 12 will require a confirmatory scan at least 6 weeks later showing two or more new bone lesions on bone scan.
- b For RECIST v1.1, see [Appendix 8](#). Up to five lesions (with a maximum of 2 lesions per organ) will be recorded as target lesions (e.g., lung, liver, adrenal, nodal).
- c Confirmation must occur at the next available scan regardless of whether the patient will continue study treatment.
- d For confirmation, at least two of the lesions first identified as new must be present at the next available scan.

## **Appendix 7**

### **Modified Gynecologic Cancer InterGroup (GCIG) Guidelines**

#### **GCIG GUIDELINES FOR RESPONSE USING CA-125 (ADAPTED FOR USE IN THIS TRIAL)**

Gynecologic Cancer InterGroup (GCIG) cancer antigen 125 (CA-125) definitions are available at <http://gcig.igcs.org/CA-125.html>.

To be evaluable for response by CA-125 requires at least one pre-treatment sample  $> 2 \times$  upper limit of normal (ULN) and two post-treatment samples confirming a response.

A response to CA-125 has occurred if there is at least a 50% decrease as the result of the treatment. The pre- or post-treatment samples must satisfy the following criteria:

1. There must be at least one sample that is  $> 2 \times$  ULN prior to initiation of treatment.
2. The second sample (post-treatment) must be  $\leq 50\%$  of the pre-treatment sample.
3. The confirmatory third sample must be  $\geq 21$  days after the second sample and  $\leq 110\%$  of the second sample.
4. Any intervening samples between samples 2 and 3 must be  $\leq 110\%$  of the previous sample unless considered to be increasing because of tumor lysis.

Patients are not evaluable by CA-125 if they have received mouse antibodies or if there has been medical or surgical interference with their peritoneum or pleura during the previous 28 days.

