### **3.1.3 Tumor-Response Assessment**

For all patients with breast and ovarian cancer, tumor response will be evaluated according to RECIST v1.1. For patients with ovarian cancer, CA-125 response will be assessed according to Gynecologic Cancer InterGroup (GCIG) criteria. For patients with prostate cancer, tumor response and PSA response will be evaluated according to PCWG3 criteria.

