### **6.4 EFFICACY ANALYSES**

Efficacy analyses will include all evaluable patients, defined as all patients who receive any amount of study treatment.

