#### **6.4.1 Primary Efficacy Endpoint for Patients with Prostate Cancer**

For patients with prostate cancer, PSA response rate is defined as the proportion of patients achieving a PSA decline  $\geq 50\%$  from baseline. Patients without a post-baseline PSA assessment will be considered non-responders. The PSA response rate will be calculated, and the 95% CI will be estimated using the Clopper-Pearson method.

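### Appendix 7 makes CA-125 evaluability depend on a confirmed response and conflicts with the all-treated definition in Sections 6 and 6.4, so any CA-125 rate computed on its denominator would be overstated

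*Combined protocol and SAP*

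**What the plan says.** Section 3.1.3 makes the criteria operative: "For patients with ovarian cancer, CA-125 response will be assessed according to Gynecologic Cancer InterGroup (GCIG) criteria". Section 4.5.7 sends sites to Appendix 7 for them, and that appendix is headed as adapted for this trial.

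Appendix 7 first says who is evaluable. A patient needs at least one pre-treatment sample above twice the "upper limit of normal (ULN) and two post-treatment samples confirming a response". It then defines response: "A response to CA-125 has occurred if there is at least a 50% decrease as the result of the treatment", subject to four numbered criteria. Criterion 1 repeats the baseline requirement and criterion 2 sets the halving. Criterion 3 begins "The confirmatory third sample must be" and asks for a sample at least 21 days later that is no more than 110% of the second sample. Criterion 4 limits rises in between. A closing paragraph removes some patients: "Patients are not evaluable by CA-125 if they have received mouse antibodies", or if there was peritoneal or pleural interference in the previous 28 days.

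Section 6.4 uses the same word differently: "Efficacy analyses will include all evaluable patients, defined as all patients who receive any amount of study treatment". Section 6 applies that population to all analyses. For PSA, Section 6.4.1 adds a rule for missing data: "Patients without a post-baseline PSA assessment will be considered non-responders". Section 6.4.2 has the equivalent for tumor response. There is none for CA-125.

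The efficacy objectives (Sections 2.2.1 to 2.2.3) and the efficacy analyses (Sections 6.4.1 to 6.4.3) concern prostate cancer. None names a CA-125 response rate.

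**The concern.** A response rate is interpretable only if membership of the denominator is settled without reference to the outcome. Appendix 7 requires the two post-treatment samples to confirm a response before the patient counts as evaluable. A patient whose CA-125 never falls, or who leaves before a confirming sample, is then not a non-responder but absent.

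The baseline half of the sentence does little work, because Section 4.1.1 already requires ovarian patients to have CA-125 above twice ULN. Apart from the exclusions in the closing paragraph, the outcome-dependent half alone decides who is counted.

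Part 1 includes a preliminary look at anti-tumor activity (Section 3.1.1.1). As no CA-125 analysis is written into Section 6.4, Appendix 7 is the only CA-125-specific text that says who is evaluable, and whoever summarizes these data may well use it. A rate built that way would make activity in ovarian patients look better than it was.

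**Working it through.** The documents state no CA-125 rate, and no ovarian sample size within the approximately 24 patients of Part 1. There is therefore no plan figure to reproduce, and all counts below are assumptions. Let n be the number treated, x the confirmed responders and m the patients without a second post-treatment sample. Confirmed responders have two samples by definition, so m falls only among non-responders.

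**The three denominators**

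- All treated (Sections 6 and 6.4): x/n.
- Lenient reading of Appendix 7 (two post-treatment samples available, whatever they show): x/(n − m). Relative to all treated this is 1/(1 − q), with q = m/n.
- Literal reading: only patients whose samples confirm a response are evaluable, so the rate is x/x = 100% for any x of 1 or more, and undefined for x = 0. One marginal exception: if confirming covers only criteria 2 and 3, a patient failing criterion 4 could be evaluable without being a responder.

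**Illustration with n = 8, x = 3, m = 2**, using exact Clopper-Pearson intervals, the method the plan uses for PSA response and ORR:

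| Reading | Rate | 95% CI (%) |
|---|---|---|
| All treated | 3/8 = 37.5% | 8.5 to 75.5 |
| Lenient | 3/(8 − 2) = 3/6 = 50.0% | 11.8 to 88.2 |
| Literal | 3/3 = 100% | 29.2 to 100 |

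Here q = 2/8 = 0.25 and 1/(1 − 0.25) = 1.33, so the lenient rate is one third too high in relative terms.

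**Other assumed sizes**

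- n = 6, x = 2: all treated 2/6 = 33.3% (4.3 to 77.7). Lenient: 2/5 = 40.0% with m = 1, or 2/4 = 50.0% with m = 2. Literal: 2/2 = 100% (15.8 to 100).
- n = 12, x = 4: all treated 4/12 = 33.3% (9.9 to 65.1). Lenient: 4/10 = 40.0% with m = 2, or 4/8 = 50.0% with m = 4. Literal: 4/4 = 100% (39.8 to 100).

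**How large m could be on the lenient reading.** Section 4.5.7 and Appendix 1 schedule CA-125 on Day 1 of each 28-day cycle. Taking Cycle 1 Day 1 as baseline, the second scheduled Day 1 sample is at Cycle 3 Day 1, 2 × 28 = 56 days later. Appendix 1 also schedules CA-125 at the treatment discontinuation visit, within 30 days of the last dose. A patient sampled at Cycle 2 Day 1 who stops before Cycle 3 can therefore still have two post-treatment values. Moreover, all ovarian patients are in Part 1 and start ipatasertib on Day −7, so the Cycle 1 Day 1 sample might itself be counted as post-treatment. Both points make m smaller than the Day 1 schedule alone suggests. Neither changes the literal result.

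**The case against.** The strongest reply is that there is no CA-125 rate to distort. No objective or analysis section plans one, and Section 6 allows listings in place of tables when numbers are small, as they may be for ovarian patients. A listing has no denominator. This stands: the bias is conditional on a rate being reported.

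A second reply is that Sections 6 and 6.4 already supply the denominator, under which nothing is inflated. That is a possible outcome, but the documents give no order of precedence, and Appendix 7 is the more specific text with its own definition of evaluable.

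A third is that the literal reading is unlikely to be intended. Response is defined separately, and the closing paragraph on who is not evaluable does not list lack of response. That is fair, and 100% is better seen as what the sentence implies than as a forecast. The sentence still says what evaluability requires, and the lenient reading also departs from Section 6.4.

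A reader might infer more, and the documents do not support it:

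- That everyone who stops before Cycle 3 Day 1 is lost. The discontinuation sample contradicts this.
- That admitting platinum-resistant patients brings more early stopping. Section 1.1.1 says only that response rates to PARP inhibitors are higher in platinum-sensitive disease.
- That the PSA rule in Section 6.4.1 is breached. It is specific to PSA, and extending it to CA-125 would be a new rule.
- That activity in ovarian patients rests on CA-125 alone. They must have measurable disease and are also assessed by RECIST v1.1.

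**Conclusion.** The point holds in conditional form. Appendix 7 ties evaluability to the outcome and conflicts with Sections 6 and 6.4, and the conflict is unresolved. If a CA-125 rate is computed on the Appendix 7 denominator, it is 100% by construction on the literal wording, apart from the criterion 4 exception. On the lenient wording it is too high by the factor 1/(1 − q), where q is the share of treated patients without a second sample. If Section 6.4 governs, there is no inflation.

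The illustrated rates rest on assumed numbers of patients, responders and early losses. A reader might infer that the trial's efficacy results are inflated. That does not follow: no primary or secondary endpoint, sample size or dose-selection rule uses CA-125 response. What is at risk is the descriptive reading of Part 1 ovarian data. The correction is cheap and worth making before those data are summarized.

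**What to change.** Replace the evaluability sentence in Appendix 7 with: *Evaluable for CA-125 response: all treated ovarian patients with a pre-treatment CA-125 > 2 × ULN who do not meet the exclusions below; patients without post-treatment samples meeting criteria 2–4 are counted as non-responders.* Keep criteria 2 to 4 as the definition of response only.

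Add a sentence to Section 6.4 stating that this denominator applies to any CA-125 rate reported. This is needed because the listed exclusions mean that it can still differ from all treated patients. Say there too whether such a rate will be reported.

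While editing, reconcile the baseline sample. Appendix 7 wants it before treatment starts, but Appendix 1 marks CA-125 first at Cycle 1 Day 1, after the seven-day ipatasertib run-in, with no mark at screening. The entry criterion already requires a CA-125 value, so a usable baseline may exist.

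The cost is a sentence or two in each place and no additional post-treatment sampling. The downside is that any CA-125 rate reported will be lower than on the Appendix 7 denominator.
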